1 PROTOCOL SUMMARY

1.1 Synopsis

Protocol title: A phase 3, multicenter, randomized, double-blind, placebo-controlled, parallel group study to evaluate the efficacy and safety of bimekizumab in adult Korean study participants with moderate to severe plaque psoriasis

Short title: A randomized, double-blind, placebo-controlled study to evaluate the efficacy and safety of bimekizumab in adult Korean study participants with moderate to severe plaque psoriasis

Rationale: The purpose of this study is to evaluate the efficacy and safety of bimekizumab in adult Korean study participants (aged at least 19 years) with moderate to severe plaque psoriasis (PSO). Following the completion of the pivotal global Phase 3 program of bimekizumab in moderate to severe PSO, the aim of this study is to bridge the existing evidence of efficacy and safety of bimekizumab from the Phase 3 program with limited Korean participation to a Korean population of study participants with moderate to severe PSO.

Objectives and endpoints

Objectives	Endpoints
Primary	Co-Primary Endpoints
To evaluate the efficacy of bimekizumab compared with placebo	
Co-Primary Endpoint 1:
 
 Participant-level outcome: Psoriasis Area and Severity Index (PASI)90 response at Week 16 
Co-Primary Endpoint 2:
 
 Participant-level outcome: Investigator’s Global Assessment (IGA) 0/1 (clear or almost clear with at least a 2-category improvement from Baseline) response at Week 16
Secondary	
To evaluate the efficacy of bimekizumab compared with placebo at achieving complete skin clearance (PASI100/IGA 0)	
 Participant-level outcome: PASI100 response at Week 16 Participant-level outcome: IGA 0 (clear with at least a 2-category improvement from Baseline) response at Week 16
To evaluate the efficacy of bimekizumab compared with placebo at achieving rapid response (PASI75)	
 Participant-level outcome: PASI75 response at Week 4

Objectives	Endpoints
To evaluate the efficacy of bimekizumab compared with placebo on itch, pain, and scaling	
Reported by study participants using the patient symptom diary (PSD) (also published as Patient Symptom and Impact Measure [P-SIM] [Gottlieb et al, 2020]):
 
 • Participant-level outcome: PSD (P-SIM) response for itch at Week 16 • Participant-level outcome: PSD (P-SIM) response for pain at Week 16 • Participant-level outcome: PSD (P-SIM) response for scaling at Week 16
To evaluate the efficacy of bimekizumab compared with placebo on the change in psoriatic scalp disease in study participants with scalp psoriasis (PSO) at Baseline	
 • Participant-level outcome: Scalp IGA 0/1 (clear or almost clear with at least a 2-category improvement from Baseline) response at Week 16 for study participants with scalp PSO at Baseline
To assess the effect of bimekizumab compared with placebo on quality of life (QOL)	
 • Participant-level outcome: Dermatology Life Quality Index (DLQI) 0/1 response at Week 16
To evaluate the effect of bimekizumab compared with placebo on percent change from Baseline in body surface area (BSA) affected by PSO	
 • Participant-level outcome: Percent change from Baseline in BSA affected by PSO at Week 16
To evaluate the safety of bimekizumab	
 • Incidence of treatment-emergent adverse events (TEAEs) throughout the study • Incidence of treatment-emergent serious adverse events (TE-SAEs) throughout the study • Incidence of TEAEs leading to permanent discontinuation of investigational medicinal product (IMP) throughout the study
To assess the effect of bimekizumab on depression occurrence or worsening	
 • Change from Baseline in Patient Health Questionnaire (PHQ)-9 at Week 16
Tertiary	
To evaluate the pharmacokinetics (PK) of bimekizumab in study participants with moderate to severe PSO	
 • Plasma bimekizumab concentrations over the study duration
To evaluate the immunogenicity of bimekizumab	
 • Anti-bimekizumab antibody status over the study duration

Objectives	Endpoints

To assess the efficacy of bimekizumab compared with placebo over time
	
 • PASI75 response over time • PASI90 response over time • PASI100 response over time • Absolute and percent change from Baseline in PASI score over time • Percentage of study participants with absolute PASI score ≤ 1, ≤ 2, ≤ 3, and ≤ 5 over time • Time to PASI50, PASI75, PASI90, and PASI100 response • IGA 0/1 response (with at least 2-category improvement from Baseline) over time • IGA 0 response (with at least 2-category improvement from Baseline) over time • Scalp-specific IGA (scalp IGA) 0/1 response (clear or almost clear with at least 2-category improvement from Baseline for participants with scalp PSO at Baseline) over time • Percentage of study participants with absolute BSA affected by PSO=0%, $\leq 1\%$, $\leq 3\%$ and $\leq 5\%$ over time • Percentage of study participants achieving a DLQI Total Score of 0 or 1 over time • Change from Baseline in DLQI Total Score over time • PSD (P-SIM) response rates over time • Change from Baseline in PSD (P-SIM) scores over time

To further evaluate the safety of bimekizumab compared with placebo over time
	
 • Selected safety topics of interest TEAEs • Change from Baseline in laboratory variables (hematology and biochemistry) • Incidence of markedly abnormal laboratory values • Change from Baseline in vital signs • Incidence of markedly abnormal vital signs • Change from Baseline in electrocardiogram (ECG) parameters • ECG outliers • Change from Baseline in PHQ-9 • Incidence of PHQ-9 scores ≥ 15 and ≥ 20 • Incidence of suicidal ideation, suicidal behavior, or self-injurious behavior without suicidal intent (from Columbia Suicide Severity Rating Scale [C-SSRS])

Overall design

PS0032 is a Phase 3, multicenter, randomized, double-blind, placebo-controlled, parallel group study to evaluate the efficacy and safety of bimekizumab compared with placebo in adult Korean study participants with moderate to severe plaque PSO.

The study population consists of adult Korean study participants (≥ 19 years of age) with a diagnosis of moderate to severe plaque PSO (Baseline PASI ≥ 12 and BSA affected by PSO $\geq 10\%$ and IGA score ≥ 3 on a 5-point scale) who are a candidate for systemic PSO therapy and/or phototherapy.

The Screening Period will last 2 weeks, but can be extended up to a total of 5 weeks in cases where a laboratory assessment needs to be repeated or to allow washout of prohibited medications. During the Screening Period, eligible study participants will be informed about the study and sign the Informed Consent Form (ICF). Following signed informed consent, all screening procedures and laboratory tests (hematology, urine, and biochemistry) will be performed per the Schedule of Activities (SoA) (Table 1-1). The Screening Period will also enable washout of any medications not permitted for use during the study. Study participants who require prophylaxis for latent tuberculosis (LTB) infection must be on treatment for at least 4 weeks prior to the first dose of IMP. These study participants may be rescreened after receiving prophylaxis treatment. One rescreening may be allowed after consultation with the Medical Monitor. Further details are provided in Section 5.4.

After completion of the Screening Period, eligible study participants will be allowed to enroll into the study. Approximately 45 adult Korean study participants will be randomized 2:1 to receive the following blinded IMP regimens during the Treatment Period:

- Bimekizumab 320mg every 4 weeks (Q4W) administered subcutaneous (sc) injection (30 study participants)
- Placebo Q4W administered sc injection (15 study participants)

During the Treatment Period, IMP will be administered at the study site.

All study participants choosing not to transition into a managed access program (MAP) (see Section 6.8) will have a Safety Follow-Up (SFU) Visit 20 weeks post last dose of IMP. Safety assessments will be made by ongoing monitoring and evaluation of adverse events (AEs) and other safety topics of interest specific to bimekizumab.

Study participants withdrawing early from IMP will undergo the Premature End of Treatment (PEOT) Visit assessments and be asked to continue in the SFU Period.

A study participant is considered to have completed the study if he/she has completed the Treatment Period of the study (Week 16) regardless of transfer into the MAP or completion of the SFU visit (see Section 6.8).

The end of the study is defined as the date of the last study participant's last visit (LPLV) in the study.

Number of participants

Approximately 45 adult Korean study participants will be randomly assigned to IMP for an estimated total of 30 evaluable study participants in the bimekizumab 320mg group and 15 study participants in the placebo group.

Treatment groups and duration

[figure not shown]
Study participants will be randomized 2:1 to 2 dose groups; bimekizumab 320mg Q4W or placebo. This study will include 3 periods: Screening Period (2 to 5 weeks), Treatment Period (16 weeks), and SFU Period (20 weeks after the last dose of IMP).

This document cannot be used to support any marketing authorization application and any extensions or variations thereof.

PUBLIC COPY

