8.2.8.1 Time period and frequency for collecting AE and SAE information

All AEs and SAEs will be collected from the signing of the ICF until the SFU Visit at the time points specified in the SoA (Table 1-1).

In order to ensure complete safety data collection, all AEs occurring during the study (ie, after the signing of the ICF), including any pretreatment and post-treatment periods required by the protocol, must be reported in the CRF even if no IMP was taken but specific study procedures were conducted. This includes all AEs not present prior to the Screening Visit and all AEs that recurred or worsened after the Screening visit.

All SAEs will be recorded and reported to the Sponsor or designee within 24 hours, as indicated in Section 10.3. The Investigator will submit any updated SAE data to the Sponsor within 24 hours of it being available.

The Investigator is specifically requested to collect and report to UCB (or its representative) any SAEs (even if the Investigator is certain that they are in no way associated with the IMP), up to 20 weeks from the final dose of IMP for each study participant, and to also inform study participants of the need to inform the Investigator of any SAE within this period. Serious AEs that the Investigator thinks may be associated with the IMP must be reported to UCB regardless of the time between the event and the end of the study.

The method of recording, evaluating, and assessing causality of AEs, SAEs and the procedures for completing and transmitting SAE reports are provided in Section 10.3.

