9.4.1 Safety analyses

9.4.1.1 AEs

Adverse events will be coded according to the Medical Dictionary for Regulatory Activities (MedDRA v19.0). Treatment-emergent AEs are defined as those AEs that have a start date on or following the first dose of IMP.

The frequency of all TEAEs will be presented for each treatment group separately by system organ class, high level term, and preferred term. The data will be displayed as number of study participants experiencing the TEAE, percentage of study participants, and number of TEAEs. Additional tables will summarize serious TEAEs, TEAEs leading to discontinuation, TEAEs by severity, and TEAEs categorized as safety topics of interest and AESIs. Definitions for categorizing TEAEs as safety topics of interest and AESIs will be provided in the SAP.

Further details of TEAE summaries will be provided in the SAP.

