- The Investigator may change his/her opinion of causality in light of follow-up information and send a SAE follow-up report with the updated causality assessment.
- The causality assessment is one of the criteria used when determining regulatory reporting requirements.

Follow up of AEs and SAEs

- The Investigator is obligated to perform or arrange for the conduct of supplemental measurements and/or evaluations as medically indicated or as requested by UCB to elucidate the nature and/or causality of the AE or SAE as fully as possible. This may include additional laboratory tests or investigations, histopathological examinations, or consultation with other health care professionals.
- An AE should be followed until it has resolved, has a stable sequelae, the Investigator determines that it is no longer clinically significant, or the study participant is lost to follow up. This follow-up requirement applies to AEs, SAEs, and AEs of special interest.
- If a study participant dies during participation in the study or during a recognized follow-up period, the Investigator will provide UCB with a copy of any postmortem findings including histopathology.
- New or updated information will be recorded in the originally completed eCRF.
- The Investigator will submit any updated SAE data to the UCB within 24 hours of receipt of the information.

Reporting of SAEs

SAE reporting to UCB via an electronic data collection tool

- The primary mechanism for reporting an SAE to UCB will be the electronic data collection tool.
- If the electronic system is unavailable for more than 24 hours, then the site will use the paper SAE data collection tool (see next section).
- The site will enter the SAE data into the electronic system as soon as it becomes available.
- After the study is completed at a given site, the electronic data collection tool will be taken off-line to prevent the entry of new data or changes to existing data.
- If a site receives a report of a new SAE from a study participant or receives updated data on a previously reported SAE after the electronic data collection tool has been taken off-line, then the site can report this information on a paper SAE form (see next section) or to the UCB Study Physician by telephone.

Contacts for SAE reporting can be found in [SERIOUS ADVERSE EVENT REPORTING](#)

This document cannot be used to support any market authorization application and any extensions or variations thereof.

PUBLIC COPY

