ion An AE is any untoward medical occurrence in a subject or clinical investigation subject administered a pharmaceutical product that does not necessarily have a causal relationship with this treatment. An AE can therefore be any unfavorable and unintended sign (including an abnormal laboratory finding), symptom, or disease temporally associated with the use of a medicinal (investigational) product, whether or not related to the medicinal (investigational) product. Adverse events will be coded according to the Medical Dictionary for Regulatory Activities (MedDRA version 19.0).

5.6.2.1 **Data considerations**

Treatment-emergent AEs are defined as those AEs that have a start date on or following the first dose of IMP through the to the end of the time at risk, as defined in section 5.6.

The rules for imputing partial start or stop dates are outlined in 5.1.1.7.3. If it is not possible (due to partial dates) to determine whether an AE is treatment-emergent then it will be assumed to be a TEAE. If the intensity of an AE is unknown, it will be considered as severe. If the relationship to study drug is missing, it will be considered as related.

Treatment-emergent AEs will be summarized as study participant incidence (number and percentage of study participants experiencing the AE) and AE frequencies (number of AEs including repeat events) by treatment group.

Selected AE summaries will include the exposure-adjusted incidence rate (EAIR) and the exposure-adjusted event rate (EAER). The 95% CIs will be reported for the EAIR only.

The EAIR is the total number of study participants with a specific AE divided by the total time at risk across all study participants. If a study participant has multiple events, the time of exposure is calculated to the first occurrence of the AE being considered. If a study participant has no events, the total time at risk is used. The EAER is the total number of AEs including repeat occurrences in individual study participants divided by the total time at risk across all study participants. Exposure adjusted rates (EAIR and EAER) will be scaled to 100 participant-years. Study participant time at risk represents the time a participant is at risk for having an AE. These definitions will be used in calculations of exposure-adjusted rates for adverse events.

Details of the calculations for exposure adjusted rates (EAIR and EAER) can be found in section 6.1.5.2

The following PTs will be used to classify COVID-19 adverse events:

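### TEAEs are defined by start date alone, so an AE that begins in Screening and worsens or becomes serious after first dose can drop out of the secondary AE endpoints

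*Protocol*

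**What the plan says.** The Protocol synopsis lists three secondary safety endpoints based on AEs: "Incidence of treatment-emergent adverse events (TEAEs) throughout the study", "Incidence of treatment-emergent serious adverse events (TE-SAEs) throughout the study" and "Incidence of TEAEs leading to permanent discontinuation of investigational medicinal product (IMP) throughout the study".

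Protocol 9.4.1.1 gives the definition: "Treatment-emergent AEs are defined as those AEs that have a start date on or following the first dose of IMP". SAP 5.6.2.1 repeats the rule ("Treatment-emergent AEs are defined as those AEs that have a start date on or following the first" dose) and closes the window at the end of the time at risk. Neither text mentions a change in intensity or seriousness.

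On collection, Protocol 8.2.8.1 has AEs recorded from signature of the consent form to the SFU Visit. On the length of the pre-dose window, the synopsis says: "The Screening Period will last 2 weeks, but can be extended up to a total of 5 weeks". Section 8.2.8.1 also makes reportable "all AEs that recurred or worsened after the Screening visit".

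On recording, Protocol Appendix 3 (follow-up of AEs and SAEs) says: "New or updated information will be recorded in the originally completed eCRF". Protocol 10.1.6.1 leaves detailed entry instructions to eCRF Completion Guidelines, which are not part of the documents reviewed.

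**The concern.** A start-date rule works if every on-treatment deterioration receives its own start date. It fails where a deterioration is entered as an update to an event that began before dosing. The event then keeps a pre-dose start date, and its later severity, seriousness or link to IMP discontinuation does not reach the TEAE tables.

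Deterioration on treatment is what these endpoints are meant to show. The fungal infection, opportunistic infection, malignancy, hypersensitivity and hepatic tables (SAP 5.6.2.3) also draw on TEAEs, and Protocol 10.1.10 names TEAEs and TE-SAEs as the events to be published on registries. In a multicentre trial, whether such an event is counted could depend on site data-entry habits.

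**Working it through.** The plan gives no figure for this point. Its one design calculation, the power for PASI90, does not depend on the TEAE definition. The check is therefore a reading of the definition against the collection and recording rules, followed by a statement of scale.

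**Step 1. Apply the rule to each case of an AE that starts in Screening.**

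- It worsens after first dose and the site opens a new record dated at the worsening: the start date is post-dose, so it is a TEAE.
- It increases in intensity and the site updates the existing entry: the start date stays pre-dose, so it is not a TEAE.
- It becomes serious and the site updates the existing entry: it is not a TE-SAE.
- It worsens, IMP is permanently stopped, and the site updates the existing entry: it is absent from the table of TEAEs leading to discontinuation. It is still in the summary of discontinuations due to AEs on the Randomized Set (SAP 5.2), which has no TEAE restriction.
- It does not change but IMP is stopped: it is not a TEAE, which is reasonable, but the same two tables differ.

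**Step 2. Compare with how the SAP treats uncertain events.** Under SAP 5.6.2.1, an AE whose status cannot be settled because of partial dates is assumed to be a TEAE, unknown intensity is taken as severe, and a missing relationship is taken as related. Under SAP 5.1.1.7.3 a wholly unknown start date is first set to the date of dosing. Uncertainty is thus resolved towards counting, whereas a documented deterioration on an updated entry is not counted.

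**Step 3. Scale.** Inputs are the planned 30 bimekizumab and 15 placebo participants (Protocol 9.8).

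- One omitted participant on bimekizumab: 1/30 = 3.3 percentage points.
- One omitted participant on placebo: 1/15 = 6.7 percentage points.
- If an arm has one TE-SAE or one discontinuation due to a TEAE, omitting it makes the reported incidence 0.

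**Step 4. How likely is at least one case?** The documents give no rate of Screening-onset AEs that later worsen. For an assumed per-participant probability q, the chance of at least one case among 45 is 1 − (1 − q)^45:

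- q = 1%: 1 − 0.99^45 = 36%
- q = 2%: 1 − 0.98^45 = 60%
- q = 5%: 1 − 0.95^45 = 90%

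These show sensitivity to an assumption and are not estimates. They are also upper limits for a loss, because a case entered as a new record is counted.

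**The case against.** The strongest reply is that the protocol already treats worsening as an event. Appendix 3 includes exacerbated disease in the AE definition and counts both laboratory results that worsen from Baseline and exacerbations of preexisting conditions. Section 8.2.8.1 requires worsening to be reported, and section 9.4.1.4 puts clinically significant examination changes into the TEAE summary. A worsening entered with its own onset date is counted under the existing text. This stands. A reader might infer that every Screening-onset AE that worsens is lost from all three endpoints; the documents do not support that.

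The Appendix 3 sentence on updated information can also be over-read. It is general follow-up wording, sets no start-date rule and does not forbid a new AE line. The Completion Guidelines might already require one, so it cannot be said that sites receive no such instruction. This stands too, but it leaves the outcome dependent on a document outside the protocol and SAP. The reporting clauses also settle that a worsening is reported, not what start date it carries, and an AE of unchanged intensity that becomes serious is not clearly covered by them.

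Third, information survives elsewhere: discontinuations due to AEs on the Randomized Set, complete listings, 24-hour SAE reporting, and laboratory shift and markedly abnormal tables. This limits the harm but does not restore the endpoint counts. Disagreement between the disposition and TEAE-discontinuation tables is not in itself an error, since one counts AEs on the Randomized Set and the other TEAEs on the Safety Set.

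Finally, the same definition applies to both blinded arms, and eligibility rules on recent infection and unstable disease narrow the pool. Both are fair. The exclusion for active infection within 14 days of Baseline nevertheless exempts the common cold, and ALT, AST or ALP above normal but below the exclusion limit is allowed at entry (Protocol 5.2 and 5.4).

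**Conclusion.** The gap is real but conditional. Both documents define a TEAE by start date with no worsening clause, so an AE held on a single record that begins before first dose and then becomes more intense or serious on treatment is excluded by the stated rule. Whether this happens depends on how the worsening is entered, which the protocol and SAP leave open. The claim is that such events can be left out, not that they will be.

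The number affected and the arm that would lose more cannot be derived. Each omitted participant is worth 3.3 or 6.7 percentage points, assuming the planned 30 and 15 participants. Sample size, power and the co-primary analyses are unaffected. The point is worth acting on because these arms are small, serious events and discontinuations may be few, and the repair is cheap.

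**What to change.** Amend Protocol 9.4.1.1 and SAP 5.6.2.1 so that a TEAE is an AE that either

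- starts on or after first dose and within the time at risk, or
- starts before first dose and increases in intensity or becomes serious on or after first dose and within the time at risk.

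Three rules should accompany the second limb:

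1. **Onset date.** Use the date of worsening as onset for the EAIR and EAER. The EAIR in SAP 6.1.5.2 counts exposure up to the first occurrence, so a pre-dose start date would give zero or negative time.
2. **Count once.** If the eCRF guidelines require a new record dated at the worsening, only that record counts. Otherwise the EAER, which counts every AE, could include the same worsening twice.
3. **Unchanged pre-dose AEs.** Do not call an AE treatment-emergent only because IMP was stopped. Report these cases separately, so that the disposition and TEAE-discontinuation tables can be reconciled.

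State the recording convention in the eCRF guidelines if it is not already there. If sites update the existing entry, check that the eCRF captures the date of the change, because the second limb cannot be programmed without it.

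The cost is a short text change in each document and minor extra programming. A few more events may count as treatment-emergent, which is the cautious direction for safety. No added visit or clinical rule is needed.
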